### **Assessments of Adverse Events**

Each adverse event will be assessed for severity, causality, seriousness and expectedness as described below.

**Severity** 

	Category	Definition
/	ASD - vivomixx protocol v6 .docx, IRAS 204582, Version 6.0, 30/01/2020, Page 33 of 57	

Mild	The adverse event does not interfere with the participant's daily routine, and does not require further intervention; it causes slight discomfort
Moderate	The adverse event interferes with some aspects of the participant's routine, or requires further intervention, but is not damaging to health; it causes moderate discomfort
Severe	The adverse event results in alteration, discomfort or disability which is clearly damaging to health

### Causality

The assessment of relationship of adverse events to the intervention is a clinical decision based on all available information at the time of the completion of the case report form.

The following categories will be used to define the causality of the adverse event:

Category	Definition
Definitely	There is clear evidence to suggest a causal relationship, and other possible contributing factors can be ruled out.
Probably	There is evidence to suggest a causal relationship, and the influence of other factors is unlikely
Possibly	There is some evidence to suggest a causal relationship (e.g. the event occurred within a reasonable time after administration of the trial intervention). However, the influence of other factors may have contributed to the event (e.g. the participant's clinical condition, other concomitant events).
Unlikely	There is little evidence to suggest there is a causal relationship (e.g. the event did not occur within a reasonable time after administration of the trial intervention). There is another reasonable explanation for the event (e.g. the participant's clinical condition, other concomitant treatments).
Not related	There is no evidence of any causal relationship.
Not assessable	Unable to assess on information available.

### **Expectedness**

Category	Definition
Expected	An adverse event which is consistent with the information about the
	intervention clearly defined in this protocol.
Unexpected	An adverse event which is not consistent with the information about the
	intervention clearly defined in this protocol.

### **Recording adverse events**

All adverse events will be recorded in the medical records in the first instance.

### Flow Chart for SAE reporting

ASD - vivomixx protocol v6 .docx, IRAS 204582, Version 6.0, 30/01/2020, Page 36 of 57

#### Unblinding

#### **Emergency unblinding:**

The trial code should only be broken for valid medical or safety reasons e.g. in the case of a severe adverse event where it is necessary for the investigator or treating health care professional to know which treatment the participant is receiving before the participant can be treated. Subject always to clinical need, where possible, members of the research should remain blinded.

The code breaks for the trial are held by the GI Physiology Unit at UCLH and are the responsibility of [name].

In the event that unblinding is required, a formal request will be made by the investigator/treating health care professional to an individual authorised and delegated to perform code break.

If the person requiring the unblinded information is a member of the Investigating team then a request to the authorised individual to unblind will be made and the treatment allocation information obtained.

If the person requiring the unblinding information is not the CI/PI then that healthcare professional will contact the Investigating team to request the code break. Unblinding will take place if in the opinion of the treating physician a patient's health is compromised. The authorised individual will break the code and immediately inform the treating healthcare professional of the participant's treatment allocation. The treating physician has the ultimate decision and right to unblind the patient.

On receipt of the treatment allocation details, the CI/PI or treating health care professional will treat the participant's medical emergency as appropriate.

The CI/PI will document the breaking of the code and the reasons for doing so on the CRF and unblinding log and will file this, in the site file and medical notes. It will also be documented at the end of the trial in any final trial report and/or statistical report.

The CI/Investigating team will notify the JRO in writing as soon as possible following the code break detailing the necessity of the code break.

The written information will be disseminated to the Data Monitoring Committee for review in accordance with the DMC Charter.

#### **Reporting Urgent Safety Measures**

If any urgent safety measures are taken the CI/ PI shall immediately and in any event no later than 3 days from the date the measures are taken, give written notice to the relevant REC and Sponsor of the measures taken and the circumstances giving rise to those measures.

#### Notification of reportable protocol violations

A reportable protocol violation is a breach which is likely to effect to a significant degree:

(a) the safety or physical or mental integrity of the participants of the trial; or

(b) the scientific value of the trial. ASD - vivomixx protocol v6 .docx, IRAS 204582, Version 6.0, 30/01/2020, Page 37 of 57

The sponsor will be notified immediately of any case where the above definition applies during the trial conduct phase.

#### **Trust Incidents and Near Misses**

An incident or near miss is any unintended or unexpected event that could have or did lead to harm, loss or damage that contains one or more of the following components:

- a. It is an accident or other incident which results in injury or ill health.
- b. It is contrary to specified or expected standard of patient care or service.

c. It places patients, staff members, visitors, contractors or members of the public at unnecessary risk.

- d. It puts the Trust in an adverse position with potential loss of reputation.
- e. It puts Trust property or assets in an adverse position or at risk.

Incidents and near misses must be reported to the Trust through DATIX as soon as the individual becomes aware of them.

A reportable incident is any unintended or unexpected event that could have or did lead to harm, loss or damage that contains one or more of the following components:

- a) It is an accident or other incident which results in injury or ill health.
- b) It is contrary to specified or expected standard of patient care or service.
- c) It places patients, staff members, visitors, contractors or members of the public at unnecessary risk.
- d) It puts the Trust in an adverse position with potential loss of reputation.
- e) It puts Trust property or assets in an adverse position or at risk of loss or damage.

#### **Data management**

#### Confidentiality

All data will be handled in accordance with the UK Data Protection Act 1998.

The Case Report Forms (CRFs) and questionnaires will not bear the participant's name or other personal identifiable data. The participant's trial identification number, will be used for identification and this will be clearly explained to the patient in the Patient information sheet. Patient consent for this will be sought.

#### Data collection tools and source document identification

Data will be collected on trial specific case report forms (CTFs) and data collection tools such as standardised questionnaires.

Source data are contained in source documents and must be accurately transcribed on to the CRF. Examples of source documents are medical records which include laboratory and other clinical reports etc.

A source document list will be implemented prior to the start of the trial to identify:

• which data is to be recorded directly onto the CRF;

- which data is recorded firstly into source documents, such as medical notes, and then transcribed into the CRF; and
- which data is not to be recorded in the CRF but only recorded in source documents, e.g. participant questionnaires.

The participant's parents will complete the Parent questionnaires while at the clinic appointments at UCLH.

The child's educator will be provided with stamped addressed envelopes to post back the completed questionnaires to the researcher.

The educator will complete the Educator questionnaires and post to the researcher using the stamped addressed envelopes provided.

We will take active measures to minimise loss to follow-up, such as back-up 'best contact' addresses, sending reminders after 2 weeks and allowing telephone completion of questionnaires at this stage. All patients will receive the treatment product at some stage of the trial, which should encourage continued involvement. All patient's parents will receive phone calls from the researcher in Week 5, 9, 21 and 25 to offer support and answer any questions.

It is the responsibility of the investigator to ensure the accuracy of all data entered in the CRFs. The delegation log will identify all those personnel with responsibilities for data collection and handling, including those who have access to the trial database.

#### Methods to protect against other sources of bias

Phone interviews and follow-up clinic interviews will explore treatment fidelity. Treatment fidelity data collected will assess compliance with treatment plan (dose, administration, whether given daily, vehicle drink or food used to deliver the treatment powder, number of unused Vivomixx/placebo sachets).

Ensuring standardisation of intervention and outcome measurement (performance bias) Standardisation of intervention delivery will be the responsibility of the researcher who has clinical expertise in this area. Parents will be given written and verbal instructions to give the age-related dose of Vivomixx/placebo daily, mixed into a cold drink or selected cold foods. The powder can be mixed into a cold drink or mixed into selected cold food such as yoghurt or fruit puree. Time of day of administration is not important and can be selected to suit the child. Compliance with these instructions will be checked at phone and clinic follow-ups throughout the trial.

Contextual data will be gathered on what drink or food is being used as a vehicle for delivery of the treatment and whether there have been any significant changes in the child's diet and any new medications or nutritional supplements will be noted.

The same researcher will conduct the interviews for all participants at all stages of the trial.

#### Detection bias

Group allocation will be concealed from the participants and the researcher. It is thought very unlikely that the participant's parents will be able to detect whether they are giving the placebo or active treatment, even if they talk to other parents in the study. The placebo product has already been used in previous clinical trials and is indistinguishable in taste and appearance from the treatment product. A collaborator will ensure completeness and accuracy of data entry of questionnaire responses to the database.

#### **Completing Case Report Forms**

All CRFs must be completed and signed by staff that are listed on the site staff delegation log and authorised by the CI/PI to perform this duty. The CI/PI is responsible for the accuracy of all data reported in the CRF.

Once completed the original CRFs are kept at site. Source data verification of a CRF page should be completed and all data queries answered prior to submission where possible.

#### Data handling

In the study, the data described in the section Trial Procedures, sub-section Subsequent assessments and procedures, will be collected from patients in accordance with the patient consent form, patient information sheet and Trial Procedures section of this protocol.

The completed questionnaires and assessments will be secured in a filing cabinet in an access-card controlled Unit at UCLH. UCL will act as the data controller of such data for the study.

[name], UCL [name], will process, store and dispose of the completed questionnaires and assessments in accordance with all applicable legal and regulatory requirements, including the Data Protection Act 1998 and any amendments thereto.

When participants have been recruited into the study and given informed consent, they will be assigned a non-identifiable code and all data (paper and electronic) will use this code. Identifiable data (e.g. contact details) will be held in a manual file that will be locked between clinics and will only be used to contact the participant about the study. All data will be held on a secure, password protected University computer.

The completed questionnaires and assessments will not be transferred to any party not identified in this protocol and are not to be processed and/or transferred other than in accordance with the patients' consent.

## **Statistical Considerations**

### **Primary Outcome**

Our primary outcome is a change in the baseline Autism Treatment Evaluation Checklist (ATEC) total score to the total score after 12 weeks and 28 weeks of treatment.

The ATEC was developed in 1999 by Bernard Rimland and Stephen M. Edelson of the Autism Research Institute, as a measure to evaluate treatment effectiveness in the ASD population. It was developed to address the need for an easy to administer, sensitive to change and valid instrument specifically developed for children with ASD.

The ATEC is a one-page form, designed to be completed by parents, teachers, or caregivers. It consists of 4 subtests: I. Speech/Language Communication (14 items); II. Sociability (20 items); III. Sensory/

ASD - vivomixx protocol v6 .docx, IRAS 204582, Version 6.0, 30/01/2020, Page 40 of 57

Cognitive Awareness (18 items); and IV. Health/Physical/Behavior (25 items). The scale covers 77 items and gives a total score and scores for each of the 4 sub-sections. The higher the score, the greater the disability overall or in a sub-section. The ATEC total score can range from 0 - 180 and is calculated by summing the scores of each subsection. Geier et al [60] compared the ATEC to the Childhood Autism Rating Scale (CARS) and found significant correlation between total ATEC and CARS scores. Many studies have successfully used the ATEC to measure treatment effects in autism or to measure the severity of autism [61][62][63][64][65][20][66][67][68].

Other instruments such as the Autism Diagnostic Interview-Revised (ADI-R), the Autism Diagnostic Observation Schedule (ADOS) and the Childhood Autism Rating Scale (CARS) have been used to assess progress or response to treatment, but these were primarily developed as diagnostic instruments and as such are designed to show overall *stability* over time and not to be sensitive to change. These measures also do not assess the physical and systemic issues in ASD. The ATEC is unique in that it does address these issues. It has recently been validated against the CARS, which is an established, professional-related measure of autism [60].

### **Secondary Outcomes**

1. A change in the frequency of GI symptoms as assessed by the Gastrointestinal History questionnaire.

A secondary outcome of this study is the postulated improvement in the participant's GI symptom frequency scores over the 12 and 28-week treatment period. Assessing the severity of symptoms in children with ASD is difficult as many are non-verbal or unable to answer questions regarding symptoms. In 2003 the Childhood Autism Risks from Genetics and the Environment (CHARGE) study [70] developed and began using a frequency assessment of GI symptoms in children with ASD, which they called the Gastrointestinal History Questionnaire. The Gastrointestinal History questionnaire (GIH) includes 10 Likert scale items for the following symptoms: abdominal pain, gaseousness/bloating sensation, diarrhoea, constipation, pain on stooling, vomiting, sensitivity to foods, difficulty swallowing, blood in stools and blood in vomit. In addition, the GIH includes four yes/no questions asking about the presence of food allergies, diet restrictions, food dislikes, and whether any GI diagnosis has ever been given. Finally there are open-ended questions asking parents to list; food allergies, reasons for diet restrictions, and what GI condition has been diagnosed. For this study, the GIH will be used by the clinician as a pro forma for interview with patients and their parents.

- A change in Aberrant Behaviour Checklist (ABC) score
   A secondary outcome of this study is the postulated improvement in the participant's behavior.
   Maladaptive behavior will be measured using five subscales of the ABC: irritability (15 items),
   lethargy/social withdrawal (16 items), stereotypy (7 items), hyperactivity (16 items) and
   inappropriate speech (4 items) as validated by Kaat et al. [59].
   This one-page, parent completed assessment is the gold standard evaluation for the assessment
   of autism severity and can also be used for assessing response to treatment interventions in
   terms of behavior.
- A change in Autism Parenting Stress Index (APSI)
   A secondary outcome is a change in the baseline APSI score to the score after 12 weeks of
   treatment and after 28 weeks of treatment.

This one-page, self-assessment questionnaire was developed and validated by Silva and Schalock in 2012 [14]. It is designed to assess parent stress in 13 aspects of autism of concern to parents and to provide a measure of parenting stress specific to core and co-morbid symptoms of autism. It reflects the time, effort and actual difficulty of parenting in the light of the physical, social and communication barriers imposed by the disability. It is intended for use by clinicians to assess the effects of intervention on parenting stress. It is designed to be completed by parents of children with ASD and asks them to rate 13 aspects of their child's health on a 0 - 5 scale according to how much stress it causes them and/or their family, (0 - Notstressful, 1 -Sometimes creates stress, 2 – Often creates stress, 3 – Very stressful on a daily basis, 5 – So stressful sometimes we feel we can't cope). It provides a total score that ranges from 0 - 65 and the higher the score, the more parenting stress. The Autism Parenting Stress Index (APSI) was used to assess the change in parental stress in a study of parent-delivered massage for ASD children [69].

- A change in clinician's global assessment
   An improvement in the researcher's global assessment of the participant after 12 weeks of treatment and after 28 weeks of treatment.
- 5. To explore parents' experience of the study and delivering the intervention to guide future research and optimize the treatment experience.

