# **Objectives**

Our primary objective is to assess the effectiveness of Vivomixx as an agent in improving overall function in children with ASD and GI symptoms.

Secondary objectives of the trial are

- $\circ$  ~ To identify changes in GI function
- To identify factors predicting outcome with this therapy so we can identify the subset of ASD children that should respond to this treatment
- $\circ$   $\;$  To identify whether the intervention reduces parenting stress
- o To explore the participant's experience of the trial

In summary, our objective is to explore the relationship between the gut microbiota and ASD core symptoms using tools known to alter the GI microbiota, and measuring outcomes using standard assessments of overall function and aberrant behaviour in children with ASDs. At the same time, we will conduct qualitative research to assess the effect of these interventions on the quality of life of the patient and their parent(s).

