The researcher will phone the participant's parent in Week 21 and Week 25. During the phone calls in Week 21 and Week 25, questions will be asked of the participant's parent to assess and encourage compliance and to check for any change in circumstances that might affect treatment efficacy. Qualitative data on their experience of the trial will also be collected by the researcher.

After 29 weeks, participants will attend UCLH for a 45-minute outpatient consultation (Visit 4). They will be asked to bring any remaining Vivomixx/placebo sachets to the consultation. During this consultation, the researcher will make a global assessment and assess the frequency of GI symptoms

using the GIH questionnaire. The participant's parent will again complete an ATEC and ABC evaluation for their child, and an Autism Parenting Stress Index questionnaire.

Both groups will have the same amount of health professional contact.

The placebo's packaging, taste and appearance of the powder will be indistinguishable to Vivomixx.

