#### **APSI**

Analyse the APSI score after treatment with the active product compared to baseline and contrast that to the score after the placebo treatment. To report what proportion and number of participants that showed a reduction in the score after active treatment, what the mean reduction was with confidence interval.

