The efficacy of the multi-strain probiotic, Vivomixx, on behaviour and gastrointestinal symptoms in children with autism spectrum disorder (ASD)

NCT03369431

18th March 2021

Statistical Analysis Plan

Principal Analysis

The principal analysis will look for between phase differences in outcome measures assuming no order of treatment effects, which will be investigated in the secondary analysis. The outcome variables consider are:

1. Change from baseline ATEC scores (**Interval Data: between groups**): **PRIMARY OUTCOME MEASURE**

Secondary measures

1. Change from baseline ABC scores (**Interval Data: between groups**)
2. Gastrointestinal events: frequency of abdominal pain, gaseousness, diarrhoea, constipation, pain on stooling, and difficulty swallowing. (**Interval Data: between groups**)
3. Bristol Stool Scale: proportion of phase participants with type 4 stool samples after active treatment. (**Dichotomous data: between groups**)
4. Clinical Global Impression (**Interval Data: between groups**)
5. Treatment Effectiveness Score (**Interval Data: between groups**)
6. Correlations: ATEC vs constipation frequency on GI History; ATEC vs diarrhoea frequency on GI History; ATEC vs ATEC components (i.e. Health/Physical/Behaviour scores); ATEC vs Clinical Global Impression. (**Interval Data: Correlation**)

All between groups interval data will be subject to the following protocol for statistical analysis.

1. Calculation of mean, standard error and median and 25-75 quartiles for both phases.
2. Kolmogorov-Smirnov test to assess normality in the between phase differences in primary and secondary outcome measure with interval measurements.
3. If there is no statistically significant ($\alpha = 0.05$) evidence of non-normality in the mean differences then a paired t-test¹ will be used to assess statistical significance.
4. If there is statistically significant ($\alpha = 0.05$) evidence of non-normality in the mean differences, then a Wilcoxon-Signed-rank-test will be used to assess statistical significance.

All between groups dichotomous data will be assessed for statistical significance by calculating the Relative Risk and corresponding 95% confidence intervals for exposure to the active agent. Corresponding p-values can, if desired, be calculated from the 95% Confidence Intervals; however, 95% Confidence Intervals that do not contain the value 1 are statistically significant at $\alpha = 0.05$.

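### The SAP omits the protocol's parenting-stress outcome (APSI) without a recorded reason, and adds or narrows other secondary measures without marking them as changes from the protocol.

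*Protocol*

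**What the plan says.** **Protocol.** One of the secondary aims under Objectives is "To identify whether the intervention reduces parenting stress". Secondary Outcomes carries this through with "A change in Autism Parenting Stress Index (APSI", measured from baseline to after 12 and 28 weeks. The APSI paragraph of the secondary outcome analysis then plans the comparison: "Analyse the APSI score after treatment with the active product compared to baseline and contrast that to the score after the placebo treatment". It also asks for the number and proportion of participants whose score fell, and the mean reduction with a confidence interval.

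The questionnaire is part of the parents' pack at visit 1 and is repeated at visits 3 and 4. For visit 4, Subsequent assessments and procedures says "The participant's parent will again complete an ATEC and ABC evaluation for their child, and an Autism Parenting Stress Index questionnaire". Appendix 1 shows the same three collections.

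The other quantitative secondary outcomes are the Aberrant Behaviour Checklist (ABC), the clinician's global assessment, and the Gastrointestinal History questionnaire (GIH), given as "A change in the frequency of GI symptoms as assessed by the Gastrointestinal History questionnaire" and described as having ten Likert items. A fifth outcome, parents' experience of the study, is qualitative.

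**SAP.** Under Principal Analysis, the numbered secondary measures are ABC, six named gastrointestinal symptoms, a Bristol Stool Scale outcome ("proportion of phase participants with type 4 stool samples after active treatment"), Clinical Global Impression, a "Treatment Effectiveness Score", and a set of correlations with ATEC. Neither APSI nor parenting stress is mentioned anywhere in the SAP.

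**The concern.** The SAP is the document an analyst works from. If it alone is followed, a stated objective gets no answer, although parents are asked to fill in the questionnaire at three visits. The protocol's APSI paragraph does not fill the gap, because it names no statistical test.

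The items that are new to the SAP stand in the same list as ABC, with nothing to mark them as later additions. A reader of the results could not tell which secondary outcomes were set at protocol stage and which came in later. For the Treatment Effectiveness Score, a reader could not even tell what was measured: the SAP says only that it is interval data compared between groups.

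**Working it through.** No sample size, power or significance figure is at issue, so the check is a comparison of lists. The inputs are the protocol's Secondary Outcomes, its secondary outcome analysis paragraphs and Appendix 1, set against the numbered secondary measures in the SAP.

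| Measure | Protocol | SAP |
|---|---|---|
| ABC | Outcome, analysis, schedule | Item 1 |
| GIH | Outcome with ten Likert items, analysis, schedule | Item 2, six symptoms |
| APSI | Objective, outcome, analysis, schedule | Absent |
| Clinician's global assessment | Outcome, analysis, schedule | Item 4, if this is the Clinical Global Impression |
| Parents' experience | Outcome, qualitative | Absent, as expected for a statistical plan |
| Bristol Stool Scale, type 4 proportion | Absent | Item 3 |
| Treatment Effectiveness Score | Absent | Item 5, not defined |
| Correlations with ATEC | Not an outcome | Item 6 |

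**Dropped.** APSI is 1 of the 4 quantitative protocol secondary outcomes (GIH, ABC, APSI, global assessment).

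**Added.** Of the SAP's five group-comparison items (ABC, GI symptoms, Bristol, global impression, Treatment Effectiveness Score), 2 are new. With the correlations, 3 of the 6 numbered items are new. The Bristol scale and the Treatment Effectiveness Score appear in none of the protocol's outcomes, analyses, visit procedures, schedule or glossary. The protocol does collect stool samples, but its Stool Microbiome Analysis section describes 16S rRNA sequencing and no stool typing.

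**Narrowed.** Of the ten GIH items, the SAP keeps abdominal pain, gaseousness, diarrhoea, constipation, pain on stooling and difficulty swallowing. It leaves out vomiting, sensitivity to foods, blood in stools and blood in vomit: 10 − 6 = 4 items.

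**Timing.** The protocol's section on sensitivity and other planned analyses foresees a more detailed SAP. That SAP may be updated at blind review and is to be final before the blind is broken, with formal records of both events. The SAP carries the date 18 March 2021. It does not say whether the blind was intact on that day.

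**The case against.** The strongest reply is that the protocol itself announced a later, more detailed SAP, open to revision at blind review. A change of measures made under the blind is not improper. The protocol's APSI paragraph has also not been withdrawn, so the APSI analysis is not shown to have been abandoned. Both points stand. They turn the criticism into one of conflict and missing documentation, but they do not remove it: adding detail does not cover leaving out an outcome without comment, and the new items carry no reason or label.

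The correlations have some root in the protocol, whose summary asks whether better function goes with fewer GI symptoms. They are still not among its listed outcomes.

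Three stronger readings are tempting, and the documents do not support them.

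- **Outcome switching that has biased the results.** This would require choosing outcomes with knowledge of results by arm. Neither document says that the blind was broken before the SAP was written, or that the new items were put in to replace APSI.
- **The SAP date shows a change after the trial had ended.** The study timetable has the last patient finishing treatment in the week of 1 October 2018. But the protocol was still being amended on 30 January 2020, so that timetable is a poor guide to the real end. What matters is timing relative to unblinding, which is not stated.
- **A false-positive cost of 9.75%.** This is 1 − 0.95² = 0.0975 for two added independent tests of true null hypotheses. It ignores the test that was dropped and the tests already there. If each of the six symptoms is tested separately, the group comparisons number 1 + 6 + 1 + 1 + 1 = 10 with the two additions and 8 without. Under the same independence assumption, the chance of at least one false positive goes from 1 − 0.95⁸ = 33.7% to 1 − 0.95¹⁰ = 40.1%, about 6.5 points, and restoring APSI would raise it further. Such figures describe a secondary family for which no multiplicity adjustment is stated. They do not measure the harm from this mismatch.

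**Conclusion.** The mismatch is real, and nothing in either document resolves it. One of the four quantitative protocol secondary outcomes, tied to a stated objective, has no place in the SAP. Three of the SAP's six numbered secondary items are not protocol outcomes, one of them is undefined, and the GIH has lost four of its ten items. No reason is recorded for any of this. Selective reporting is therefore a risk that the documents leave open, not something they establish.

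The conclusion rests on two assumptions. First, the Clinical Global Impression is taken to be the protocol's clinician's global assessment; if it is not, the mismatch is larger. Second, APSI is taken to have been collected as scheduled; the documents show the plan, not the data. The title and signature pages are not available here, so the lack of a finalisation record in the available text is not itself counted against the plan.

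The point concerns secondary outcomes only. The primary outcome, its test and the sample size are untouched. The change should be made, but the main result does not depend on it.

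**What to change.** 1. Add APSI to the SAP's secondary measures, analysed by the same within-child Vivomixx-versus-placebo comparison as ABC. Report alongside it the proportion with a lower score and the mean reduction with its confidence interval, as the protocol's APSI paragraph already asks. A dated and justified removal before unblinding would also end the conflict between the documents, but it would leave the objective unanswered.
2. Move the Bristol Stool Scale outcome, the Treatment Effectiveness Score and the correlations to a section labelled as exploratory additions not in the protocol.
3. Define the Treatment Effectiveness Score: source, rater, range and time points. A label alone does not make it interpretable.
4. Give the reason for reducing the GIH from ten items to six.
5. Record when each of these changes was made relative to unblinding, in line with the records the protocol calls for.

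The cost is SAP wording and one further analysis of data the protocol already schedules. No new data collection is needed.
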